5.11 Adherence and retention

Two important goals of this protocol are to optimize adherence to the pharmacological regimen and to maximize the retention of participants in the study. Assessment of adherence to the assigned study medication will provide clinic staff a means to identify participants having problems with adherence. Adherence will be assessed by:

- Counts of capsules in the patient's returned medication bottles
- Conducting a brief, structured interview, in which the study coordinator will assist the patients to identify problems in taking the study medication and to estimate adherence to the prescribed medicine since their previous visit.

These assessments will guide the consideration of strategies to improve adherence. Resources will be provided to remove barriers to participation such as child or elder care, transportation, and parking expenses. These resources can be provided as cash, transportation vouchers, or parking passes. An honorarium may be paid to patients in recognition of their time and effort twice during the trial when scheduled visits and procedures are completed successfully. Certificates of appreciation may be given at enrollment and at conclusion as an incentive.

5.12 Management of concomitant conditions

Hypertension, hyperlipidemia and diabetes will be managed in conjunction with the patient's primary care physician according to the protocols described in the Standard of Care document prepared by the Standard of Care Committee of the NASH CRN. Pregnancy will be managed according to the guidelines described in section 5.15.

In the event of major dermatological reactions such as generalized urticaria, bullous rashes, exfoliative dermatitis, or Stevens-Johnson Syndrome, study medication will be discontinued immediately and not restarted. For local skin reactions, study medication may be discontinued if the skin reactions are potentially drug related. If the rashes clear, the study medication may be restarted.

If local skin reactions recur with restarting the study medication, study medication should be discontinued. In cases where the study medication has been discontinued, the study medication will be unmasked and the participant, investigator, and the primary care provider will be notified in order to prevent future exposures.

6. Adverse event monitoring and reporting

6.1 Food and Drug Administration

The FLINT trial will be conducted under an Investigational New Drug (IND # 110354) held by the NIDDK. The investigators will complete a Statement of Investigator (FDA Form 1572) and must obtain IRB approval per the Code of Federal Regulations before the initiation of the FLINT trial. The study will not begin until the IND is in effect. The safety data required to meet IND application regulations will be collected through adverse event reporting by the clinic investigators and will be provided by the Data Coordinating Center to the NIDDK for transmission to the FDA, Steering Committee, and DSMB.

6.2 Definitions⁹²

Adverse event means any untoward medical occurrence associated with the use of a drug in humans, whether or not considered drug related.

Life-threatening adverse event or life-threatening suspected adverse reaction. An adverse event or suspected adverse reaction is considered "life-threatening" if, in the view of either the investigator or sponsor, its occurrence places the patient or subject at immediate risk of death. It does not include an adverse event or suspected adverse reaction that, had it occurred in a more severe form, might have caused death.

Serious adverse event or serious suspected adverse reaction. An adverse event or suspected adverse reaction is considered "serious" if, in the view of either the investigator or sponsor, it results in any of the following outcomes: Death, a life-threatening adverse event, inpatient hospitalization or prolongation of existing hospitalization, a persistent or significant incapacity or substantial disruption of the ability to conduct normal life functions, or a congenital anomaly/birth defect. Important medical events that may not result in death, be life-threatening, or require hospitalization may be considered serious when, based upon appropriate medical judgment, they may jeopardize the patient or subject and may require medical or surgical intervention to prevent one of the outcomes listed in this definition.

Suspected adverse reaction means any adverse event for which there is a reasonable possibility that the drug caused the adverse event. For the purposes of IND safety reporting, "reasonable possibility" means there is evidence to suggest a causal relationship between the drug and the adverse event. Suspected adverse reaction implies a lesser degree of certainty about causality than adverse reaction, which means any adverse event caused by a drug.

Unexpected adverse event or unexpected suspected adverse reaction. An adverse event or suspected adverse reaction is considered "unexpected" if it is not listed in the investigator brochure or is not listed at the specificity or severity that has been observed. "Unexpected," as used in this definition, also refers to adverse events or suspected adverse reactions that are mentioned in the investigator brochure as occurring with a class of drugs or as anticipated from the pharmacological properties of the drug, but are not specifically mentioned as occurring with the particular drug under investigation.

6.3 Adverse event reporting

The FLINT trial investigators and staff will monitor and report adverse events to ensure patient safety. There are two separate sets of government regulations that apply to unanticipated or adverse events in research studies: (1) 45 CFR Part 46, Subpart A; the "Common Rule",⁹³ shared by 17 Departments and Agencies and (2) 21 CFR 312,⁹² the FDA regulation for adverse events. The Common Rule requires written procedures and policies for ensuring reporting of "unanticipated problems" involving risks to

participants to IRBs, appropriate institutional officials, and the Department or Agency Head. The FDA regulation requires notification of the FDA and participating investigators of any adverse event associated with the use of a test article that is “both serious and unexpected.” Investigators should refer to the FDA guidance *Improving Human Subjects Protection*,⁹⁴ for adverse events reportable to their IRB. Since the definitions and reporting requirements for unanticipated events differ between the two sets of Federal regulations, the FLINT trial definitions and procedures for adverse events are designed to satisfy both sets of requirements.

Summary data on adverse events will be monitored by the DSMB quarterly and at its semiannual meetings or more frequently, as needed. These summaries will include analyses comparing rates of adverse events by treatment group, by clinic, or in other subgroups requested by the DSMB. Where applicable, signs and symptoms associated with the adverse event will be graded as to severity by the clinical site staff as mild, moderate, or severe using Version 3.0 of the National Cancer Institute’s Common Terminology Criteria for Adverse Events (CTCAE).⁹⁵

After each DSMB meeting, the NIDDK will issue a written summary of the review of the study data, including adverse events, for transmission to the IRBs at each of the study centers. Analyses or listings of adverse events will not be provided to the IRBs; however, adverse events involving unanticipated problems involving risks to participants, or breaches of protocol which might entail risk to participants must be reported to local IRBs as soon as possible after they are discovered. Each participating center is responsible for ensuring that all local IRB requirements for reporting adverse events are met.

Reporting adverse events

Adverse events will be recorded on study data forms whether or not they are thought to be associated with the study or with the study drug. Adverse events may be discovered during regularly scheduled visits or through unscheduled patient contacts between visits. It is the responsibility of the clinical center principal investigator to determine if an adverse event is reportable to their local IRB. Events threatening the integrity of the study, or well-being of the participant should be reported to the Data Coordinating Center by completing and keying the Interim Event Report (IE) form. If the adverse events have a CTCAE Severity Grade of 3 (Severe), or higher, then a copy of the Interim Event Report (IE) should also be emailed or faxed to the Data Coordinating Center for review by the NASH CRN Safety Officer, [name], within 1 week. A summary of adverse events will be reported to the FDA as part of the IND Annual Report.

6.4 Reporting serious adverse events

Serious adverse events (SAE) must be reported upon discovery at the clinical center. This will involve completing an Interim Event Report (IE) data form describing the severity and details of the event. If the SAE is judged by the study physician to be unexpected and potentially caused by the FLINT study drug, then the investigator must also submit an SAE/IND Safety Report (SR) form, along a narrative summarizing the circumstances of the event, the current status of the patient, and a copy of the IRB submission to the Data Coordinating Center for review by the NASH CRN Safety Officer, [name] and within two working days. Within three days, the DCC will notify the sponsor, NIDDK, and submit a preliminary report for further review of the material of the SAE. If deemed necessary, NIDDK will notify Intercept Pharmaceuticals within 1 week. NIDDK will inform DSMB members of the SAE per their charter.

Expedited IND Safety Report

If the NIDDK Program Official determines that the SAE requires an expedited IND Safety Report, then

the NIDDK program official or the NIDDK Regulatory Affairs Specialist will notify the FDA no more than 15 calendar days from the initial receipt of the SAE (no later than 7 days if the SAE is fatal or life threatening). Intercept Pharmaceuticals will receive a copy of the expedited IND Safety Report that is submitted to the FDA. . If the FDA determines that a change the investigator’s brochure, IND or protocol is needed, the DCC will send a copy of the IND Safety Report to all clinical centers with instructions to forward the report to their IRB.

Follow-up IND Safety Report

Within one month of the initial expedited IND Safety Report, NIDDK will submit a Follow-up IND Safety Report to the FDA. The Data Coordinating Center will work the clinical center to obtain additional information and to report the details of the disposition of the SAE. The clinical center investigator may also be responsible for completing an FDA MedWatch 3500 form. Intercept Pharmaceuticals will receive a copy of the Follow-up IND Safety Report that is submitted to the FDA..

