5.10 Safety issues

Obeticholic acid

The latest version of the OCA Investigator's Brochure⁸³⁾ provides details about the safety profile of obeticholic acid obtained from clinical trials. This will be updated during the study as appropriate and in conformance with the appropriate FDA regulations. The investigators should be familiar with the safety profile of the drug.

To date the following AEs of note have been seen:

Normal Volunteers: Single doses up to 500 mg and multiple doses up to (and including) 250 mg (20 and 10x the dose used in this study, respectively) were administered. At the 100 mg daily dose, modest elevations in both ALT and AST were observed. At 250 mg, reversible elevations in ALT and AST (to a maximum of 5x ULN) were seen. Pruritus was experienced by half of the volunteers at 250 mg.

Primary Biliary Cirrhosis: In a 3 month, placebo controlled study in PBC patients evaluating 10 mg, 25 mg, and 50 mg of OCA pruritus was the only common AE clearly related to OCA use. The frequency of pruritus was higher at both the 25 mg and 50 mg doses and the severity of pruritus was worse in all 3 OCA treated groups (placebo group: 50%; OCA groups: 47-85%); 24% of the patients receiving 50 mg were discontinued from the study due to pruritus (which is the most common symptom in this cholestatic disease). Nausea (generally mild) was the only other AE seen in all three treatment groups more frequently than for placebo. Three patients at 50 mg had serious hepatic AEs (SAEs); two developed increases in bilirubin and liver enzymes which were considered likely related to OCA therapy. The other patient developed a bleed from previously existing esophageal varices. All of these patients recovered. The 50 mg dose is not considered a likely appropriate starting dose in cholestatic liver diseases. Subjects without severe pruritus at lower doses are likely to tolerate higher doses if titrated up.

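### Section 6.4 makes sending the expedited IND Safety Report to the clinical centers depend on an FDA-determined document change, while section 6.3 says investigators must be notified of every serious, unexpected drug-associated event

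*Protocol*

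**What the plan says.** Protocol section 6.3 (Adverse event reporting) sets the standard: "The FDA regulation requires notification of the FDA and participating investigators of any adverse event associated with the use of a test article", where the event is serious and also unexpected. It names two recipients, the FDA and the participating investigators, and attaches no further condition. The same paragraph adopts the standard for this trial, saying that "the FLINT trial definitions and procedures for adverse events are designed to satisfy both sets of requirements".

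Protocol section 6.4 (Reporting serious adverse events) gives the procedure. Once the NIDDK program official determines that an event needs an expedited report, NIDDK "will notify the FDA no more than 15 calendar days from the initial receipt of the SAE", or within 7 days if the event is fatal or life threatening. The manufacturer "will receive a copy of the expedited IND Safety Report that is submitted to the FDA". The sentence about the sites opens "If the FDA determines that a change the investigator" (a word or two is missing there) and ends by saying that if a change to the brochure, "IND or protocol is needed, the DCC will send a copy of the IND Safety Report to all clinical centers", with an instruction to forward it to their IRBs. No time limit is given for that step. For the later report, "NIDDK will submit a Follow-up IND Safety Report to the FDA" within one month, again with a copy to the manufacturer. The centers are not listed as recipients.

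**The concern.** The two sections sit next to each other and disagree about who is told. Section 6.3 makes notice to investigators depend on the nature of the event. Section 6.4 makes it depend on what the FDA later decides about documents. An event can be serious, unexpected and suspected to be drug-related without leading to a change in the brochure, IND or protocol. For such an event the procedure names the FDA and the manufacturer as recipients, but not the physicians giving the drug at the other centers.

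This matters because section 3.3 justifies the vanguard design by the lack of human data on the drug as a treatment for NASH, and treatment lasts 72 weeks. Section 5.10 adds that "The investigators should be familiar with the safety profile of the drug". That sentence contradicts nothing in 6.4, but it assumes that new safety information reaches the investigators.

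**Working it through.** No formula, sample size or error rate bears on this point, and the plan states no figure to reproduce. The check compares the texts.

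**Step 1. Recipients under the standard and under the procedure.**

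| Recipient | Section 6.3 (standard) | Section 6.4 (expedited report) | Section 6.4 (follow-up report) |
|---|---|---|---|
| FDA | Must be notified | Always, within 15 days (7 if fatal or life threatening) | Yes, within one month of the first report |
| Manufacturer | Not mentioned | Copy of the report, no condition | Copy of the report |
| Participating investigators / clinical centers | Must be notified | When the FDA determines a change to the brochure, IND or protocol is needed; no deadline | Not listed |

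The third row is where the two sections part.

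**Step 2. Does another section supply the missing notice?** Each possible route was read for two features: does it reach every site investigator, and does it concern the individual event?

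- Section 6.1: safety data go through NIDDK to the FDA, the Steering Committee and the DSMB. Site investigators are not named and no timing is given.
- Section 6.3: after each DSMB meeting a written summary goes to the IRBs, but analyses and listings of adverse events are excluded.
- Section 6.3: unanticipated problems must go to local IRBs promptly once discovered. A center cannot report another center's event unless it has been told of it.
- Section 5.10: the Investigator's Brochure is updated as appropriate. This is not notice of an individual event. Section 6.2 defines an unexpected event as one not listed in the brochure at the specificity or severity observed, so the brochure in hand cannot by definition have described it.
- Section 7.6: the DSMB sees serious adverse events as they occur, and NIDDK passes DSMB recommendations to investigators as appropriate. This conveys recommendations, at discretion, rather than the event.

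None has both features. The conditional sentence in 6.4 is the only stated route by which the report reaches all centers.

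**Step 3. Extent.** The synopsis and section 4.1 give 8 clinical centers. For an event at one center, 8 − 1 = 7 others have no stated direct notice if no document change follows. This is an upper limit, because some sites may learn of the event indirectly.

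**Step 4. Is the text current?** The document history (10.5) records that the May 2013 version clarified and expanded the adverse event procedures. The sentence is part of the current protocol.

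**The case against.** The strongest reply is that 6.4 says when a report will be sent and does not forbid sending it at other times. The sentence may have been meant to govern only reports that go out for IRB forwarding, with the duty in 6.3 still in force. This stands in part: the text does not prove that sites would be kept in the dark. But 6.4 is where the procedure is fixed, and staff who follow it exactly would not meet 6.3.

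The indirect routes in sections 5.10, 6.1, 6.3 and 7.6 are real safeguards. They do not guarantee notice to every investigator, but they rule out some stronger conclusions that a reader might draw:

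- *That the other sites necessarily go on dosing in ignorance, or that reports are never sent.* The documents show the absence of a stated direct notice, which is less than that.
- *That some 245 of 280 patients are affected (7 centers × 35).* This assumes equal and complete accrual at the time of the event and no information by any other route. The protocol gives no expected number of expedited reports and no share that would lead to a document change, so the product does not measure an effect.
- *That adverse event ascertainment becomes uneven and biases the comparison.* Section 6.3 requires adverse events to be recorded whether or not they are thought drug-related, treatment is masked (6.5) and randomization is stratified by center (3.2). The documents show no path to a difference between arms.

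It is also fair to object that 6.3 gives no deadline for telling investigators. The 7- and 15-day limits in 6.4 apply to the FDA, and nothing in 6.3 expressly covers follow-up reports. Sending every report on to every IRB would sit badly with 6.3, which leaves the decision on local IRB reportability to the center's principal investigator. These points limit the remedy and leave the contradiction in place.

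**Conclusion.** The point holds as a contradiction within the protocol on a patient-safety procedure. Section 6.3 states an unconditional duty to notify participating investigators of serious, unexpected, drug-associated events and says the trial's procedures meet it. Section 6.4 provides for that notice in one circumstance, without a deadline. As written, up to 7 of 8 centers have no stated direct notice of such an event when no change to the brochure, IND or protocol follows.

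The conclusion rests on two readings: that the conditional sentence in 6.4 is the only stated route to all centers, which the search of the other sections supports, and that 6.3 states the protocol's own standard, so no outside regulation need be consulted. It is wrong as written, and is more than a detail left for another document. Sample size, power, type I error and the primary analysis are not affected.

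**What to change.** Reconcile 6.4 with 6.3:

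- Remove the FDA-determination condition for notifying investigators. State that the DCC sends each expedited IND Safety Report to all clinical centers within a time limit set by the sponsor. The protocol gives no figure for this limit, so the sponsor has to choose one.
- Preferably send the follow-up report to the centers as well. This goes beyond what 6.3 expressly requires.
- State that the copies sent to sites keep treatment assignment masked from site staff.
- Leave the decision on local IRB reportability with each center's principal investigator, as 6.3 has it. Keep the existing instruction to forward the report to IRBs for cases where the brochure, IND or protocol changes, and repair the missing wording in that sentence.

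The cost is about one paragraph of protocol text and one DCC e-mail to the centers per report. No patients, visits or analyses are added.

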6.5 Procedures for unmasking treatment assignment

Treatment assignments are double masked throughout the study until all data collection for the trial has been completed and the database of trial data is officially “locked” for analysis (i.e., after completion of the 24 week post trial follow-up for all patients and entry of all data). Every effort will be made to maintain the masking throughout the study except in emergency situations. The code of specific pharmacological treatment will not be broken without the knowledge of the clinical center’s principal investigator.

In unforeseen situations where the clinical center principal investigator considers unmasking is in the best interest of the participant’s health and well-being, unmasking may be performed. In such circumstances, the NASH CRN Executive Committee will be notified within one working day. Unmasking of study medication may occur under the following conditions:

Severe allergic reaction (Stevens-Johnson Syndrome): Study medication is stopped indefinitely. The patient, primary care provider (PCP), local principal investigator and pharmaceutical manufacturer may be unmasked.

Pregnancy during the study: Study medication will be stopped indefinitely, and the coded medication will be unmasked. The patient, PCP, and investigator may be notified of the assigned treatment and the associated risks of teratogenicity.

The Data and Safety Monitoring Board will review all instances of unmasking that occur.

7. Statistical design and analysis

7.1 Hypotheses and outcome measures

Primary Hypothesis

Obeticholic acid at 25 mg orally once daily for 72 weeks is better than placebo in improving liver histologic parameters as measured by the NAFLD activity score in patients with biopsy evidence of nonalcoholic steatohepatitis.

The ***primary outcome measure*** requires the following two conditions:

- No worsening of the fibrosis score
- A decrease in NAS by 2 or more points

Secondary Hypotheses

- Administration of the farnesoid X receptor ligand obeticholic acid for 72 weeks to subjects with biopsy evidence of nonalcoholic steatohepatitis will result in improvement in insulin sensitivity as measured by HOMA-IR and the adipo-IR index.
- Administration of the farnesoid X receptor ligand obeticholic acid for 72 weeks to subjects with biopsy evidence of nonalcoholic steatohepatitis will result in reduction in MRI-determined hepatic fraction.
- Administration of the farnesoid X receptor ligand obeticholic acid for 72 weeks to subjects with biopsy evidence of nonalcoholic steatohepatitis will result in a greater decrease in the proportion of patients with a biopsy diagnosis of definite or probable NASH compared to placebo
- Administration of the farnesoid X receptor ligand obeticholic acid for 72 weeks to subjects with biopsy evidence of nonalcoholic steatohepatitis will result in reduction in serum aminotransferase and gamma-glutamyl transpeptidase.

Secondary outcome measures

- Change in histological diagnosis from NASH or indeterminate for NASH to not-NASH
 - Whereas the primary endpoint is based on changes of specific features of NASH as summed in the NAS, it does not actually evaluate whether NASH resolves with treatment. Thus this essential secondary endpoint of determining whether NASH resolves with treatment will be a major outcome of the trial.
 - It will be anticipated that some subjects judged to have NASH on their locally read entry biopsy will not have NASH on central reading of deeper cuts from the same block.
 - For the purposes of this analysis, subjects with borderline NASH will be included with subjects with definite NASH.
- Mean changes in NAS
- Changes in individual histological characteristics:
 - Mean fibrosis score
 - Change from stage 1b to 1a fibrosis
 - Steatosis
 - Lobular inflammation
 - Portal chronic inflammation
 - Ballooning
 - Other specific features from the histologic scoring system
- Changes in serum aminotransferase levels:
 - Mean change in ALT, AST, and GGT
 - Normalization of ALT or AST using two absolute values to define normality (< 40 U/L and <30 U/L for men and <40 U/L and <19 U/L for women) and GGT (using local upper limits of normal)
 - Time-dependent decline in serum mean ALT, AST, and GGT
- Changes in serum CK-18 fragment assay

- Changes in bile acids
- Changes in FGF-19 levels
- Changes in free fatty acids and adipo-IR (fatty acids x insulin)
- Changes in MRI-determined variables in the subset of patients who meet eligibility requirements and undergo MRI evaluation
 - MRI-determined hepatic fat fraction
- Changes in HRQOL
- Changes in anthropometric measures

